7.2 BACKGROUND

Chronic obstructive pulmonary disease(COPD) is a leading cause of morbidity and mortality worldwide and results in an economic and social burden that is both substantial and increasing. COPD prevalence, morbidity and mortality vary across countries and across different groups within countries[[P12-01205](#)].

The prevalence of COPD in Korea increased from 12.5% in 2011 to 13.7% in 2012 and 12.8% in 2013. The Korean National Health and Nutrition Examination Survey(KNHANES, 2013) reported that approximately 12.8% of the population who were ≥ 40 years old. In addition, 27.7 of 100,000 persons die because of respiratory diseases, including COPD which was the fifth leading cause of death in Korea(Statistics Korea, 2009).

COPD is the result of cumulative exposure over decades; often, the prevalence of COPD is directly related to the prevalence of tobacco smoking, although in several countries, outdoor, occupational and indoor pollution are major risk factors.

The prevalence and burden of COPD are projected to increase in the coming decades due to continued exposure to COPD risk factors and the changing age structure of the world's population, with more people living longer and therefore expressing the long-term effects of exposure to COPD risk factors[[P12-01205](#)].

The combination of Tiotropium and Olodaterol in a single Respimat® Inhaler device provides a rational target for optimizing bronchodilator treatment of COPD.

Tiotropium(18 μ g) inhalation powder capsule (Spiriva®) has been approved in more than 100 countries worldwide as an antimuscarinic bronchodilator with a once daily posology. An alternative aqueous formulation for use in the Respimat® device (tiotropium 5 μ g qd) has recently been approved in Europe and Japan. Olodaterol, a long acting $\beta 2$ -agonist in clinical development(Phase III) by Boehringer Ingelheim, has a clinical profile with a 24-hour duration of action. The recently completed Phase III clinical program in COPD showed that Olodaterol at doses of 5 μ g and 10 μ g once daily is safe, well tolerated and efficacious; Olodaterol 5 μ g was identified as the optimal choice of dose for once daily maintenance

bronchodilator treatment in patients with COPD[[U04-0202](#)].

Safety data from the supportive Phase III 12 week trial and the 6-week crossover trials were consistent with the data from the 52-week pooled dataset. In conclusion, Tiotropium + Olodaterol 5/5 μ g and Tiotropium + Olodaterol 2.5/5 μ g delivered via the RESPIMAT inhaler were safe and well-tolerated in patients with moderate to very severe COPD[[c01735808-12](#)].

7.3 INDICATIONS

A maintenance bronchodilator treatment to relieve symptoms in adult patients with chronic obstructive pulmonary disease(COPD).

8. RESEARCH QUESTION AND OBJECTIVES

8.1 PRIMARY OBJECTIVE

The primary objective of this study is to monitor the safety profile of Vahelva® Respimat® (tiotropium + olodaterol fixed dose combination 2.5µg/2.5µg per puff (2 puffs comprise one medicinal dose)) in Korean patient with COPD in a routine clinical setting.

8.2 SECONDARY OBJECTIVE

The secondary objective of this study is to monitor the effectiveness of Vahelva® Respimat® (tiotropium + olodaterol fixed dose combination 2.5µg/2.5µg per puff (2 puffs comprise one medicinal dose)) by evaluation the change from baseline to outcome in the (pre-dose) FEV₁(Forced Expiratory Volume in one second), (Post Bronchodilator Predicted %) FEV₁(Forced Expiratory Volume in one second) and mMRC(Modified Medical Research Council) scale of Korean COPD patients.

9. RESEARCH METHODS

This rNIS is an observational prospective, non-interventional, open-label, multi-centre and national study. As per regulation, the re-examination period extends from 31 August 2015 until 30 August 2021. However, active enrolment is to be initiated in 2016 after finalizing the re-imbursement agreement with the authority. Before initiation of the study, any newly reported adverse events collected from other sources such as spontaneous cases, literature cases etc will be closely monitored. The last patient follow up is expected in August 2021.

This study will be carried out in the manner of successive survey that the investigator will be asked to successively write in the case report forms(CRFs) from the subject who was initially administered the drug following the study start date to the requested number of subjects without omission. Prior to initiation of the study, written contract shall be concluded, and this contract shall be concluded with the head of the site or the investigator with his/her consent.

Patients will be managed according to the local practice guidelines. The choice of treatment will be solely at the discretion of the participating physician. Vahelva® Respimat® will be administered according to the approved label in Korea. Hence there are no additional risks to patients by participating in this rNIS.

9.1 STUDY DESIGN

This is a NIS based on newly collected data with Vahelva® Respimat®. Vahelva® Respimat® will be prescribed according to the local label and at the discretion of the treating physician. Since this is a NIS, the drug will not be supplied by the sponsor. Furthermore, the sponsor will not cover the expenses related to other medications taken by the patient, interventions, procedures or diagnostic test.

9.1.1 Method of assigning patients to treatment groups

The choice of treatment is fully at the discretion of the physician and the patient. There is no treatment assignment by a third party.

9.1.2 Dosage and Administration

The starting dose is based on the current authorized label in Korea. The recommended dose for adults is 5 microgram Tiotropium and 5 microgram Olodaterol given as two puffs from the Respimat® inhaler once daily at the same time of the day(see Instructions for Use).

9.1.3 Concomitant therapy, Restrictions, And rescue

The protocol will allow additional drugs considered necessary for the patient's welfare to be prescribed at the discretion of the treating physician. It is required, however, to record the details of all concomitant medication administered to the patient during the course of treatment in eCRF. This includes concomitant therapies started one month prior to Vahelva® Respimat® initiation until the patient completes the final follow-up visit.

9.1.3.1 Rescue medication, emergency procedures, and additional treatments

Please refer to the current local label.

9.2 SETTING

As per regulations, enrolled patients will be followed up for 24 weeks or 52 weeks treatment period. There will be a visit window of ±2 weeks.

9.2.1 Study sites

A total of 3,000 patients will be enrolled at approximately 50 sites by as many as 50 or more NIS physicians. To minimize the selection bias at the site level, the goal is to have participating centers reflect a balance between general hospitals and clinics for surveillance. The treating physicians will mainly be Respiratory Internists. To minimize the selection bias, consecutive patients from each site who meet inclusion criteria will be enrolled in this study.

9.2.2 Study population

9.2.2.1 Main diagnosis for study entry

Patients diagnosed with COPD will be included.

9.2.2.2 Inclusion criteria

- Patients who are new initiators of Vahelva® Respimat® in accordance with the approved label in Korea
- Age ≥ 18 years at enrolment
- Patients who have signed on the data release consent form

9.2.2.3 Exclusion criteria

- Patients with hypersensitivity to Vahelva® Respimat® or to any of the excipients.
- Patients with a history of hypersensitivity to atropine or its derivatives (e.g. ipratropium, oxitropium, glycopyrronium, aclidinium, umeclidinium)
- Patients with asthma
- Current participation in other clinical trials
- Patients for whom Vahelva® Respimat® is contraindicated according to the local label of Vahelva® Respimat®

9.2.2.4 Subjects of special investigation

The patient who have signed on the data release consent form, subjects of special investigation(Pediatric or Adolescent(Younger than 18 years), Geriatric(Older than 65 years), Pregnant Women, renal impairment, hepatic impairment and other special population) among the patients who conducted investigation for safety assessment after the administration of Vahelva® Respimat® can be further investigation into cases collected from this study may be taken into account according to the outcome of retrospective analysis.

9.2.3 Study visits

9.2.3.1 Screening and run-in periods

This section is not applicable as this is a non-interventional study.

9.2.3.2 Visit 1 - Baseline Visit

Upon patient enrolment, the following will be recorded on the patient's eCRF.

- Visit date
- Informed consent form: Date of Informed consent
- Diagnosis: Date of the diagnosis of COPD
- Inclusion / Exclusion criteria
- Demographic data: Initial, year of birth(age), gender, pregnancy, previous allergy, height, weight, smoking status
- Medical history: history of cardiovascular disease, metabolic disease, respiratory disease, any malignancy, renal dysfunction and other concomitant disease within 6 months.
- Physical examination: Blood pressure, pulse rate, body temperature
- PFT value for diagnosis of COPD: FEV₁/FVC predicted (%), (pre-dose) FEV₁ (within 6 months(180 days) prior to baseline date)
- Effectiveness outcomes : (pre-dose) FEV₁, (Post Bronchodilator Predicted %) FEV₁, mMRC scale(within 1 month(30 days) prior to baseline date)
- Concomitant medications: Record all medications have been taken at least once since one month(30 days) prior to the baseline visit.
- Dose of Vahelva® Respimat® given

At visit 1, the patient will be requested to contact the treating physician in the event of any adverse events noted after initiating Vahelva® Respimat® treatment.

9.2.3.3 Visit 2 - 24±2 weeks from Visit 1

After 24±2 weeks from Visit 1, the patients will return for follow-up. The followings will be noted and recorded in the eCRF.

- Visit date
- Physical examination: Blood pressure, pulse rate, body temperature
- Effectiveness assessment: (pre-dose) FEV₁, (post bronchodilator predicted %) FEV₁, mMRC scale
- Any change of Vahelva® Respimat® given
- Concomitant medications including new medications taken since last visit : any change in the concomitant medications(dose and dosing intervals)
- Any changes in laboratory tests if there is any lab result which was clinically significant compared to data before Vahelva® Respimat® therapy (This data is collected on the basis of medical need, i.e. independent of the NIS)
- Any adverse events noted
- Study completion status

- Overall evaluation
- NIS physician's electronic signature for data integrity(if applicable)

9.2.3.4 Visit 3 - 52±2 weeks from Visit 1

After 52±2 weeks from Visit 1, the patients will return for follow-up. The followings will be noted and recorded in the eCRF.

- Visit date
- Physical examination: Blood pressure, pulse rate, body temperature
- Effectiveness assessment: (pre-dose) FEV₁, post bronchodilator predicted %) FEV₁, mMRC scale
- Any change of Vahelva® Respimat® given
- Concomitant medications including new medications taken since last visit: any change in the concomitant medications(dose and dosing intervals)
- Any changes in laboratory tests if there is any lab result which was clinically significant compared to data before Vahelva® Respimat® therapy (This data is collected on the basis of medical need, i.e. independent of the NIS)
- Any adverse events noted
- Study completion status
- NIS physician's electronic signature for data integrity

9.2.3.5 End of study and follow-up period

Patients with adverse events noted at the final follow-up visit or upon premature discontinuation of Vahelva® Respimat® will be monitored further until the resolution of those adverse events. Alternatively, those patients will be followed up until the NIS physician and sponsor agree that no further follow-up is necessary.

9.2.4 Study discontinuation

[REDACTED] reserves the right to discontinue the study overall or at a particular study site at any time for the following reasons:

- Emergence of any effectiveness/safety information that could significantly affect continuation of the study
- Violation of applicable local regulations, the NIS protocol, or the contract by a study site or participating physician, disturbing the appropriate conduct of the study.

9.3 VARIABLES

9.3.1 Safety

9.3.1.1 Outcome(s) of safety

All reported adverse events in patients who take at least once of Vahelva® Respimat® will be noted.

Outcomes pertaining to safety will be presented as incidence rates of adverse events and will include:

- Adverse events
- Unexpected adverse events
- Serious adverse events
- Adverse Drug Reactions
- Adverse events leading to discontinuation
- Adverse events by intensity, outcome of the events, causality

9.3.2 Effectiveness

9.3.2.1 Outcome(s) of effectiveness

9.3.2.1.1 Main outcome

- Change from baseline in (Post Bronchodilator Predicted %) FEV₁ after 24 weeks and/or 52 weeks of treatment

9.3.2.1.2 Other outcomes

- Change from baseline in Pre-dose FEV₁ after 24 weeks and/or 52 weeks of treatment
- Change from baseline in mMRC score after 24 weeks and/or 52 weeks of treatment
- Overall evaluation(Improved, unchanged, aggravated or unassessable) by investigator based on overall clinical assessment including change from baseline in effectiveness assessment((Post bronchodilator predicted % of) FEV1, (pre-dose) FEV₁, mMRC scale) after 24 weeks or 52 weeks of treatment. 'Improved' is assessed as "Effective", 'Unchanged, Aggravated' are assessed as "Invalid".

9.3.2.2 Assessment of Effectiveness

- Post Bronchodilator Predicted % FEV1(Forced Expiratory Volume in one second): Post BD FEV1 should be collected within 1 month(30 days) prior to baseline and after 24 weeks and/or 52 weeks of treatment.
- (pre-dose) FEV₁ (Forced Expiratory Volume in one second): (pre-dose) FEV₁ should be collected within 1 month(30 days) prior to baseline and after 24 weeks and/or 52 weeks of treatment.
- mMRC scale: mMRC scale should be collected within 1 month(30 days) prior to baseline and after 24 weeks and/or 52 weeks of treatment.
- Overall evaluation: Overall evaluation will be assessed after 24 weeks or 52 weeks of treatment.

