9.3.3.4 Drug administration status

Information on the drug administration status includes:

- Dose
- Unit
- Start date
- Date of discontinuation or continuation

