9.3.4.1.5 Number of cases subject to effectiveness evaluation

These cases include those who signed the informed consent form to participate in this study as subject, visited as per the study schedule, took Vahelva® Respimat®, the cases included in safety evaluation, and were evaluated for the effectiveness including overall evaluation(if the case assessed as 'unassessable' will be excluded).

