9.7 DATA ANALYSIS

The safety evaluation will be performed on the “safety set” that will include all patients who have received treatment of Vahelva® Respimat® at least one time except those who are found to have no observation after enrolment, invalid registration, or invalid contract with the site. The effectiveness evaluation will be performed on the “effectiveness set”, a subset of the safety set, which will include all patients in the “safety set” except those who have no available effectiveness data and/or who do not suffer from COPD.

Medico-pharmaceutical assessment will be described with results of multiple regression analysis, 95% confidence intervals of every sub-analysis items of safety and effectiveness assessment.

Details are provided in the Statistical Analysis Plan (SAP).

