9.9 LIMITATIONS OF THE RESEARCH METHODS

9.9.1 Follow up loss

All efforts will be made to minimize lost to follow up, particularly in the tracking of lost patients. To the extent possible, occurrence of adverse event, at minimum, for patients lost to follow up will be obtained. This allows assessing the impact of informative censoring due to treatment discontinuation. Also, patients lost to follow up will be characterized compared to the remaining patients and reason and time point of loss to follow up will be evaluated.

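### The effectiveness rate covers only rated patients: those who stop Vahelva before their first effectiveness visit and go unrated leave the denominator under both definitions of the effectiveness set

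*Combined protocol and SAP*

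**What the plan says.** **Timing.** The flow chart (4.1), the visit lists (9.2.3) and section 9.3.2.2 place the post-baseline effectiveness measures at weeks 24±2 and 52±2, marked as applicable only where available. For the rating: "Overall evaluation will be assessed after 24 weeks or 52 weeks of treatment". For the main outcome: "Post BD FEV1 should be collected within 1 month(30 days) prior to baseline and after 24 weeks and/or 52 weeks of treatment". Section 9.2 states that "enrolled patients will be followed up for 24 weeks or 52 weeks treatment period".

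**Stopping.** Section 9.2.3.5 provides for follow-up of adverse events after premature discontinuation. It does not mention an effectiveness rating. The drug record (9.3.3.4) holds "Date of discontinuation or continuation", without a reason.

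**Scoring.** In section 9.3.2.1.2 'Improved' is 'Effective', while "Unchanged, Aggravated' are assessed as" 'Invalid'.

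**Who is counted.** Section 9.3.4.1.5 takes patients who "visited as per the study schedule, took Vahelva® Respimat®, the cases included in safety evaluation, and were evaluated for the effectiveness including overall evaluation", and leaves out the unassessable. Section 9.7 takes the safety set "except those who have no available effectiveness data and/or who do not suffer from COPD". Section 9.7.4 then gives a rate with a 95% interval. Section 9.7.6 works from available data and names imputation only for adverse-event dates.

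**Loss to follow-up.** Section 9.9.1 says that, as far as possible, "occurrence of adverse event, at minimum, for patients lost to follow up will be obtained". Sections 9.7.3 and 9.9.1 add a comparison of lost patients with the rest, and the reason and time of loss.

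**The concern.** In a single-arm study of a maintenance inhaler, stopping because symptoms did not improve is itself an effectiveness result. Here it can only be recorded as one if the patient is later rated at a scheduled visit. A patient who stops at, say, week 8 and does not return for a rating is neither 'Effective' nor 'Invalid'; the patient is simply absent from the rate.

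There is a second gap. Visits are timed from Visit 1, so a patient who has stopped and moved to another drug can still attend and be rated. No analysis rule keeps that rating apart from ratings made on Vahelva.

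At stake is how the secondary, effectiveness results can be read. A reader would naturally take the rate as applying to Korean patients started on the drug, whereas it applies to those who reached a visit and were rated. The confidence interval reflects sampling error only and does not show the difference.

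**Working it through.** **Step 1: follow one patient through the rules.** The patient starts Vahelva, has at least one follow-up contact, stops before week 22, and is never rated.

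- 9.2.3.5: adverse events are followed; no rating is called for.
- 9.3.2.1.2: there is no observed category, so the patient cannot be 'Invalid'.
- 9.3.4.1.5: not seen on schedule and not evaluated, so out.
- 9.7: no effectiveness data, so out.
- 9.7.6: nothing puts the patient back.
- 9.7.3 and 9.9.1: if lost to follow-up, the patient is described, but the effectiveness denominator is unchanged.

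The two set definitions differ in wording but agree on this patient.

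**Step 2: size.** The plan states no effectiveness rate, stopping rate or power, so there is no figure of its own to reproduce on this point. Everything below rests on assumed values:

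- r = share 'Effective' among rated patients
- d = share of all patients who stop and go unrated
- s = share of those stoppers who in fact benefited

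Rate over all patients = r(1 − d) + s·d. Excess of the reported rate = (r − s)·d.

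With r = 80% the reported rate is 80% in every cell by construction. The rate over all patients is:

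| d | s = 0 | s = 40% | s = 50% | s = 80% |
|---|---|---|---|---|
| 10% | 72% | 76% | 77% | 80% |
| 20% | 64% | 72% | 74% | 80% |
| 30% | 56% | 68% | 71% | 80% |

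For example, 0.80 × 0.90 + 0.50 × 0.10 = 0.77. At d = 10% and s = 0, the excess is 6 points for r = 60% and 9 points for r = 90%.

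**Step 3: compare with the planned interval.** Half-width = 1.96 × √[r(1 − r) / (N(1 − d))].

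- N = 3,000 (section 9.5), r = 80%, d = 10%: 1.96 × √(0.16 / 2,700) = 1.5 points. The excess at s = 0 is 8 points.
- N = 600, the long-term minimum in section 9.5 (20% of 3,000): 1.96 × √(0.16 / 540) = 3.4 points.
- With r = 80% and s = 0, the excess passes the half-width once d is above about 1.8% (54 of 3,000), or about 4.1% (25 of 600).

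**The case against.** **What stands against the point.**

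- The study is descriptive, effectiveness is the secondary objective, and the rating is listed among the other outcomes in 9.3.2.1.2. No test is invalidated. This limits the weight of the point, but the rate and its interval are still planned outputs.
- Section 9.7 defers details to a statistical analysis plan, and the case report form is an attachment. Neither text is in the document reviewed. A rule or a reason field there would close part of the gap.

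**Stronger readings that a reader might infer, and that the documents do not support.**

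- *All early stoppers leave the rate.* Visits run from Visit 1, so a stopper who attends can be rated. The exclusion concerns those who are not rated.
- *The problem must be worse in the 52-week group.* The flow chart also gives these patients a week-24 visit, and 9.7.4.1 uses the last follow-up visit for FEV1. A patient who stops between weeks 24 and 52 can keep week-24 data under 9.7, although the on-schedule wording of 9.3.4.1.5 might exclude that patient and the later failure is not counted.
- *The bias can only be upward.* It is upward only if unrated stoppers did worse than rated patients. People also stop for other reasons, and with s = r there is no bias.
- *Only adverse events are known for early leavers.* Section 9.9.1 sets these as a minimum and adds the reason and time of loss. Section 9.3.1.1 lists adverse events leading to discontinuation, and the visit lists record study completion status. None of these supplies an effectiveness outcome.
- *Ratings made on another drug cannot be recognised.* Stop dates (9.3.3.4) and concomitant-drug dates (9.3.3.3) are collected. What is missing is the rule for using them.

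**Conclusion.** The point holds for patients who stop before their first effectiveness visit and are not rated. Both set definitions remove them, and the plan offers no second analysis that puts them back. The planned rate is thus conditional on having been rated. Separately, a rating made after the drug was stopped is not distinguished from one made on it.

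The size is unknown, because the documents give no stopping share and no outcome for stoppers. On the assumed 80% among the rated and 10% stopping unrated, the overstatement runs from 8 points (no stopper benefited) to none (stoppers did as well as the rest), against an interval half-width of 1.5 points at N = 3,000. If stoppers did better than the rest, the sign would reverse. This is a cheap improvement to the reporting of a secondary objective. It does not touch the primary, safety objective.

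**What to change.** **In section 9.7.4**, keep the evaluated-only rate and add beside it, by follow-up group:

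1. The rate over all safety-set patients with COPD, with unrated patients who stopped counted as 'Invalid' and labelled as a lower bound with respect to stoppers. State how patients unrated for other reasons, including the unassessable, are handled, and show their number.
2. The number excluded from the effectiveness set by recorded reason, using adverse events leading to discontinuation, study completion status and the reason for loss to follow-up. Include treated patients who fall outside the safety set because they had no observation after enrolment, since item 1 does not recover them.
3. A flag for ratings dated after the recorded stop date, reported separately.

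Sections 9.3.4.1.5 and 9.7 should be reconciled at the same time, so that the evaluated-only rate has one denominator.

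**Cost.** One extra table and a less favourable second rate. Stop dates, visit dates and completion status are already collected, so no new procedure is needed.

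**Optional.** For patients still on treatment, record the overall evaluation and the reason at the contact where the drug is stopped. This would capture later stops only. Version 2.0 is dated 08 October 2020 and data collection ends on 30 August 2021. A week-50 visit by that end date implies enrolment by about 14 September 2020 (350 days earlier). Any long-term patient who can complete was therefore enrolled before this version, and stops already made would be missed.
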